6.2 Analysis of other efficacy variables

The following efficacy endpoints along with their observed values will be summarized by age group (< 65; ≥ 65 years) and overall using descriptive statistics:

- Change from baseline (mean of the 2 PSG nights at Visit 3) to Month 1 (mean of the 2 PSG nights at Visit 6) and Month 3 (mean of the 2 PSG nights at Visit 8) in Total Sleep Time (TST).
- Change from baseline^a to Month 1^b and Month 3^c in subjective WASO (sWASO).
- Change from baseline^a to Month 1^b and Month 3^c in subjective Latency to Sleep Onset (sLSO).
- Change from baseline^a to Month 1^b and Month 3^c in IDSIQ scores (i.e., Total score; Alert/Cognition and Mood domain scores).

^a Baseline is the mean value based on the screening sleep diary / IDSIQ entries performed at home in the 7 days immediately preceding the first PSG at Visit 3.

^b ‘Month 1’ is the mean value based on the sleep diary / IDSIQ entries performed at home in the 7 days immediately preceding the first PSG at Visit 6.

^c ‘Month 3’ is the mean value based on the sleep diary / IDSIQ entries performed at home in the 7 days immediately preceding the first PSG at Visit 8.

sWASO is the self-reported time spent awake after sleep onset as reported in item 7 of the sleep diary, i.e., the answer to the question “In total, how long did these awakenings last?”.

sLSO (in minutes) is the self-reported time to fall asleep as reported in item 5 of the sleep diary, i.e., the answer to the question “How long did it take you to fall asleep?”.

Section 10.1 explains how these endpoints are derived in the event of partially missing data.

The IDSIQ has 3 domains assessing Alert/Cognition, Mood, and Sleepiness [Table 2]. A Total score can also be obtained. For each domain, the item responses in the respective domains are summed (each item is based on a categorical scale ranging from 0 to 10). Prior to summation, items 1, 2, 8, 10 and 14 must be reversed [see Table 2 for details regarding scoring]. For the Total score, all item responses are summed.

Table 2 Insomnia Daytime Symptoms and Impacts Questionnaire description

Domain	Scoring	Minimum/Maximum Score
Alert/Cognition	Daily: Sum of Item 1*, Item 2*, Item 3, Item 9, Item 10*, Item 14*	Minimum score: 0 Maximum score: 60
	Weekly Average: Mean of the daily domain score over 7 days	Higher score: greater burden of illness
Mood	Daily: Sum of Item 4, Item 5, Item 6, Item 7	Minimum score: 0 Maximum score: 40
	Weekly Average: Mean of the daily domain score over 7 days	Higher score: greater burden of illness
Sleepiness	Daily: Sum of Item 8*, Item 11, Item 12, Item 13	Minimum score: 0 Maximum score: 40
	Weekly Average: Mean of the daily domain score over 7 days	Higher score: greater burden of illness
Total score	Daily: Sum of all domains above	Minimum score: 0 Maximum score: 140
	Weekly Average: Mean of the daily domain score over 7 days	Higher score: greater burden of illness

* Item 1, Item 2, Item 8, Item 10, and Item 14 scores are reverse scored prior to summation.

A plot of the mean change from baseline over time (per week, as defined in Table 7) for sWASO, sLSO and IDSIQ scores (i.e., Total score; Alert/Cognition and Mood domain scores) will be provided together with a summary table.

The same model as for the main analysis, MMRM [Section 6.1.4], will be fitted for these efficacy endpoints. The LS mean for each treatment group will be displayed along with associated standard errors and 95% CIs. For each ACT-541468 dose level comparison with placebo, the placebo-adjusted LS mean will be displayed along with associated standard error, 95% CI and unadjusted two-sided p-value.

6.3 Analysis of exploratory variables

The following exploratory endpoints will be summarized along with their observed values at the respective time points:

- Change from baseline (mean of the 2 PSG nights at Visit 3) to Month 1 (mean of the 2 PSG nights at Visit 6) and Month 3 (mean of the 2 PSG nights at Visit 8) in WASO over time (by hour of the night and by quarter of the night).
- Change from baseline^a (Visit 3) to Month 1^b and Month 3^c in the following visual analog scale (VAS) scores collected in the sleep diary: quality of the sleep, depth of the sleep, daytime alertness and ability to function.
- Change from baseline (mean of the 2 PSG nights at Visit 3) to Month 1 (mean of the 2 PSG nights at Visit 6) and Month 3 (mean of the 2 PSG nights at Visit 8) in duration of TST in each sleep stage (S1, S2, SWS and REM) over the whole night, and for each quarter of the night.
- Change from baseline (mean of the 2 PSG nights at Visit 3) to Month 1 (mean of the 2 PSG nights at Visit 6) and Month 3 (mean of the 2 PSG nights at Visit 8) in sleep architecture assessed as percentage of TST in each sleep stage (S1, S2, SWS, and REM) over the whole night, and for each quarter of the night.
- Change from baseline (mean of the 2 PSG nights at Visit 3) to Month 1 (mean of the 2 PSG nights at Visit 6) and Month 3 (mean of the 2 PSG nights at Visit 8) in sleep onset latency.
- Change from baseline (mean of the 2 PSG nights at Visit 3) to Month 1 (mean of the 2 PSG nights at Visit 6) and Month 3 (mean of the 2 PSG nights at Visit 8) in numbers of shifts from S2, SWS or REM to S1 or awake.
- Change from baseline (Visit 3) to Month 1 and Month 3 in Insomnia Severity Index[®] (ISI[®]) scores.
 - The number (%) of subjects with ≥ 6 points decrease in ISI[®] Total score from baseline (Visit 3) to Month 1 (Visit 6) and Month 3 (Visit 8) will be tabulated.
- Change from baseline (mean of the 2 PSG nights at Visit 3) to Month 1 (mean of the 2 PSG nights at Visit 6) and Month 3 (mean of the 2 PSG nights at Visit 8) in number of awakenings (defined as the number of awakenings between first epoch and last epoch not scored wake) as measured by PSG (will be summarized for the whole night, for each quarter of the night, and for each hour of the night).
- Change from baseline^a (Visit 3) to Month 1^b and Month 3^c in number of self-reported awakenings.
- Change from baseline (mean of the 2 PSG nights at Visit 3) to Month 1 (mean of the 2 PSG nights at Visit 6) and Month 3 (mean of the 2 PSG nights at Visit 8) in Sleep Efficiency (defined as $100 \times [\text{TST (min)} / \text{time in bed (min)}]$) where time in bed is fixed to 480 min during the PSG nights.
- Change from baseline (Visit 3) to Month 1 (Visit 6 or, if that is missing, week 4 of the questionnaire) and Month 3 (Visit 8 or, if that is missing, week 12 of the

questionnaire) in Patient Global Assessment of Disease Severity (PGA-S) scores (daytime symptoms).

- Change from baseline (Visit 3) to Month 1 (Visit 6 or, if that is missing, week 4 of the questionnaire) and Month 3 (Visit 8 or, if that is missing, week 12 of the questionnaire) in Patient Global Impression of Change (PGI-C) scores (daytime symptoms).
- Change from baseline (Visit 3) to Month 1 (Visit 6 or, if that is missing, week 4 of the questionnaire) and Month 3 (Visit 8 or, if that is missing, week 12 of the questionnaire) in PGI-C scores (night-time symptoms).
- Change from baseline (Visit 3) to Month 1 (Visit 6 or, if that is missing, week 4 of the questionnaire) and Month 3 (Visit 8 or, if that is missing, week 12 of the questionnaire) in Patient Global Impression of Severity (PGI-S) scores (night-time symptoms).

^a Baseline is the mean value based on the screening sleep diary entries performed at home in the 7 days immediately preceding the first PSG at Visit 3.

^b ‘Month 1’ is the mean value based on the sleep diary entries performed at home in the 7 days immediately preceding the first PSG at Visit 6.

^c ‘Month 3’ is the mean value based on the sleep diary entries performed at home in the 7 days immediately preceding the first PSG at Visit 8.

Section 10.1 explains how these endpoints, except for ISI[®], are derived in the event of partially missing data.

Additionally, the following PSG measurements will be summarized:

- Change from baseline (mean of the 2 PSG nights at Visit 3) to Month 1 (mean of the 2 PSG nights at Visit 6) and Month 3 (mean of the 2 PSG nights at Visit 8) in duration (min) of TST in each sleep stage (S1, S2, SWS and REM) by quarter of the night.
- Change from baseline (mean of the 2 PSG nights at Visit 3) to Month 1 (mean of the 2 PSG nights at Visit 6) and Month 3 (mean of the 2 PSG nights at Visit 8) in duration (min) from lights off to the first epoch of each sleep stage (S1, S2, SWS and REM).
- Change from baseline (mean of the 2 PSG nights at Visit 3) to Month 1 (mean of the 2 PSG nights at Visit 6) and Month 3 (mean of the 2 PSG nights at Visit 8) in duration of time (min) from onset of persistent sleep (LPS) to the first epoch of REM sleep.

- Change from baseline (mean of the 2 PSG nights at Visit 3) to Month 1 (mean of the 2 PSG nights at Visit 6) and Month 3 (mean of the 2 PSG nights at Visit 8) in duration of time (min) from sleep onset (LSO) to the first epoch of REM sleep.
- Change from baseline (mean of the 2 PSG nights at Visit 3) to Month 1 (mean of the 2 PSG nights at Visit 6) and Month 3 (mean of the 2 PSG nights at Visit 8) in duration of wakefulness (min) from onset of persistent sleep (LPS) till the last epoch of sleep prior lights on.

Boxplots of the change from baseline (mean of the 2 PSG nights at Visit 3) to Month 1 (mean of the 2 PSG nights at Visit 6) and Month 3 (mean of the 2 PSG nights at Visit 8) will be provided for the following:

- Duration of TST (min) in each sleep stage over the whole night, and by quarter of the night.
- % of TST spent in each sleep stage over the whole night, and by quarter of the night.
- Latency (min) to each sleep stage over the whole night.
- Duration of REM sleep (min) by quarter of the night.
- Duration of S1 sleep (min) by quarter of the night.
- Duration of the S2 sleep (min) by quarter of the night.
- Duration of SWS sleep (min) by quarter of the night.
- WASO (min) by quarter of the night.

Boxplots will also be provided for the observed values at Baseline (mean of the 2 PSG nights at Visit 3), Month 1 (mean of the 2 PSG nights at Visit 6) and Month 3 (mean of the 2 PSG nights at Visit 8) for the % of TST spent in each sleep stage over the whole night.

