6.4 Exploratory endpoints

For each variable, multiple aspects will be considered in the analysis, in particular changes from baseline at different time points.

- WASO over time (by hour of the night and by quarter of the night) on each PSG night.
- Change from baseline (Visit 3) to Month 1 and Month 3 in SQ. SQ is the sleep quality as determined by scores on the VAS (mm) in the morning.
- Change from baseline (Visit 3) to Month 1 and Month 3 in duration of TST in each sleep stage (S1, S2, SWS and REM).
- Change from baseline (Visit 3) to Month 1 and Month 3 in sleep architecture assessed as percentage of TST in each sleep stage (S1, S2, SWS, and REM) over the whole night, and for each quarter of the night.
- Change from baseline (Visit 3) to Month 1 and Month 3 in mean numbers of shifts from S2, SWS or REM to S1 or awake.
- Change from baseline (Visit 3) to Month 1 and Month 3 in ISI[®] scores.
- Change from baseline (Visit 3) to Month 1 and Month 3 in mean number of awakenings (defined as the number of awakenings between first epoch and last epoch not scored

- wake) as measured by PSG (will be summarized for the whole night, for each quarter of the night, and for each hour of the night).
- Change from baseline (Visit 3) to Month 1 and Month 3 in mean number of self-reported awakenings.
 - Change from baseline (Visit 3) to Month 1 and Month 3 in sWASO.
 - Change from baseline (Visit 3) to Month 1 and Month 3 in Sleep Efficiency (defined as $100 \times ([TST / \text{time in bed}]$).
 - Change from baseline (Visit 1) to Month 1 and Month 3 in Patient Global Assessment of Disease Severity (PGA-S) scores (daytime symptoms).
 - Change from baseline (Visit 3) to Month 1 and Month 3 in Patient Global Impression of Change (PGI-C) scores (daytime symptoms).
 - Change from baseline (Visit 3) to Month 1 and Month 3 in PGI-C scores (night-time symptoms).
 - Change from baseline (Visit 3) to Month 1 and Month 3 in Patient Global Impression of Severity (PGI-S) scores (night-time symptoms).

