7.2 Study assessments

The mandatory study assessments are listed in [Table 1](#).

All study assessments are performed by qualified study personnel (medical, nursing, or specialist technical personnel), and are recorded in the medical history and eCRF unless otherwise specified. Study assessments performed during unscheduled visits will also be recorded in the eCRF.

The following order of assessments is recommended:

- In the evening before a PSG night:
 - Urine drug screen and alcohol test
 - IDSIQ
 - Evening questionnaire in sleep diary (including VAS)
 - PGA-S daytime symptoms (in the first evening at Visits 3, 6 and 8)
 - PGI-C daytime symptoms (in the first evening at Visits 3, 6 and 8)
 - Recording of concomitant medications
 - AEs and SAEs
 - Study drug intake (30 minutes before lights off)
- In the morning after a PSG night (subject fasted):
 - Blood samples (hematology and blood chemistry, only second morning at Visits 3, 6 and 8; PK, only second morning at Visits 6 and 8).
- In the morning after a PSG night and after completion of normal morning routine (e.g., using the bathroom, eating breakfast):
 - Vital signs
 - C-SSRS[©] (only second morning at Visits 3, 6 and 8)
 - Coding sub-test[©]
 - ISI[©] (only second morning at Visits 3, 6 and 8)
 - ESS[©]
 - SDS[©]
 - BWSQ (only second morning at Visits 3, 6, 8 and 9)
 - Morning questionnaire in sleep diary (including VAS)
 - PGI-S night-time symptoms (in the first morning at Visits 3, 6 and 8)
 - PGI-C night-time symptoms (in the first morning at Visits 3, 6 and 8)
 - Recording of concomitant medications
 - AEs and SAEs
 - Neurological examination
 - 12-lead ECG (only second morning at Visits 3 and 8)
 - Patient preferences questionnaire PAUSE (only second morning at Visit 8)

The following assessments will be analyzed by an external provider (results will be transferred to the Idorsia database and to the investigators):

- Laboratory parameters
- ECG parameters
- PSG recordings
- Questionnaires completed using a hand-held device (listed below).

If the Principal Investigator (PI) delegates any study procedure/assessment for a subject, to an external facility, he/she must inform Idorsia to whom these tasks are delegated. The set-up and oversight must be agreed upon with Idorsia. The supervision of any external facilities remains the responsibility of the PI.

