7.2.2.5 Patient Global Impression of Change (daytime symptoms)

The PGI-C (daytime symptoms) is a question concerning the change in overall severity of daytime symptoms (e.g., sleepiness) and impacts (e.g., effort to perform daily activities) that the subject may have experienced due to his/her insomnia over the 7 days preceding the PGI-C daytime symptoms compared to the week before he/she started treatment. The PGI-C daytime symptoms is a self-administered question on the hand-held device and is to be completed at Visit 3 1st evening, Visit 6 1st evening, Visit 8 1st evening, Visit 10, and weekly in the evening at home from Visit 4 until EODBT.

For further details, see [Appendix 9](#).

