7.2.2.6 Patient Global Impression of Change (night-time symptoms)

The PGI-C (night-time symptoms) is a question concerning the change in the subject’s insomnia symptoms at night (e.g., trouble falling asleep, total time asleep, or number of times they wake up) over the past week (7 nights) preceding the PGI-C night-time symptoms compared to the week before the subject started treatment. The PGI-C night-time symptoms is a self-administered question on the hand-held device and is to be completed at Visit 3 1st morning, Visit 6 1st morning, Visit 8 1st morning, Visit 10, and weekly in the morning at home from Visit 4 until EODBT.

For further details, see [Appendix 10](#).

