12.5 Change from baseline

The change from baseline is defined as post-baseline value (any assessment performed after baseline and up to EOS) minus baseline value. A positive number indicates an increase as compared to baseline.

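### The exploratory PGI-C endpoints are named as change from Visit 3, although PGI-C is itself a rating of change, so each named endpoint is a difference of two change ratings

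*SAP*

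**What the plan says.** Protocol 7.2.2.5 describes the daytime PGI-C as a question on how daytime symptoms and their effects over the preceding 7 days have changed "compared to the week before he/she started treatment". Protocol 7.2.2.6 describes the night-time PGI-C in the same way, over the past 7 nights, "compared to the week before the subject started treatment".

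Both items are answered at Visit 3 as well as during double-blind treatment. The order of assessments in Protocol 7.2 includes "PGI-C daytime symptoms (in the first evening at Visits 3, 6 and 8", with the night-time item on the first morning of the same visits.

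Protocol 6.4 names the endpoint as "Change from baseline (Visit 3) to Month 1 and Month 3 in Patient Global Impression of Change (PGI-C) scores (daytime symptoms", and gives the night-time item the same form. SAP 6.3 carries both over, as change from Visit 3 "in Patient Global Impression of Change (PGI-C) scores (daytime symptoms" and likewise for the "questionnaire) in PGI-C scores (night-time symptoms". It takes the week 4 or week 12 home questionnaire when the visit value is missing. SAP 12.5 fixes the arithmetic: "The change from baseline is defined as post-baseline value (any assessment performed after baseline and up to EOS) minus baseline value".

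Two other places matter. The opening sentence of SAP 6.3 says that observed values at each time point are summarized together with the listed endpoints. SAP 13.1 records a revised baseline visit for the PGA-S but says nothing about PGI-C.

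**The concern.** A change-from-baseline score makes sense when the baseline value describes a state, such as a severity rating. PGI-C does not describe a state. The patient has already made the comparison with the time before treatment, and the answer is that comparison. The Visit 3 answer is therefore a rating of change made during the placebo run-in. Subtracting it from a later answer compares one reported change with another, on what is presumably an ordered set of categories.

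What is at stake is interpretation. A reader of the study report who sees a PGI-C endpoint will take it as how much better or worse patients say they are since before treatment. The statistic that carries the endpoint's name does not give that.

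**Working it through.** The plan states no sample size, power or precision figure for PGI-C, so there is nothing to reproduce. The check is to apply the plan's own subtraction rule to its own description of the item.

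**Inputs**
- What a rating means: change since the week before treatment started (Protocol 7.2.2.5 and 7.2.2.6).
- Baseline visit: Visit 3 (Protocol 6.4, SAP 6.3).
- What subjects take at Visit 3: daily single-blind placebo since Visit 2, with at least 7 days of diary completed (Protocol 3.1.1.1). A Visit 3 rating other than no change is therefore possible.
- Rule: change = post-baseline value − baseline value (SAP 12.5).

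**Step 1. The derived score.** Let X be the Visit 3 rating and Y the Month 3 rating. The named endpoint is D = Y − X. D equals Y only when X is coded 0, that is, no change.

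**Step 2. Illustration.** The response options are in Appendices 9 and 10, which are not shown in the public document. Assume a coding from −3 to +3 with 0 for no change, and take a subject who rates +2 (improved) at Month 3:

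| Visit 3 rating X | Month 3 rating Y | D = Y − X |
|---|---|---|
| −1 | +2 | +3 |
| 0 | +2 | +2 |
| +1 | +2 | +1 |
| +2 | +2 | 0 |

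The same reported improvement at Month 3 yields four different endpoint values. The last row, D = 0, is also the score of a subject who reported no change at both visits (0 − 0 = 0). That tie does not depend on the assumed coding: equal ratings always subtract to zero.

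**Step 3. Does the subtraction correct anything?** Visit 3 comes before randomization at Visit 4 (Protocol 3.1.1.1), so the expected Visit 3 rating is the same in every arm. The expected difference between arms in D is then the expected difference in Y. The subtraction removes no bias, and it adds none to a comparison of means.

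**Step 4. Is change since Visit 3 available elsewhere?** Yes. The PGA-S (daytime) and PGI-S (night-time) rate severity (Protocol 7.2.2.4 and 7.2.2.7), and SAP 6.3 analyses both as change from Visit 3. The change-from-baseline form suits those two items, and they already cover day and night.

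**The case against.** The strongest reply is that the interpretable result is already planned. SAP 6.3 summarizes observed values alongside the change, so the Month 1 and Month 3 ratings will be reported by arm. SAP 10.2 supplies counts and percentages for categorical variables and means, medians and quartiles for continuous ones. A reader might infer that patient-rated change will not be reported at all; that is not so. This reply stands and limits the point to which statistic is named as the endpoint. SAP 6.3 does not say whether PGI-C is to be treated as categorical or continuous.

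A second reply is that the difference has some meaning. Run-in placebo starts at Visit 2, and subjects are not told of the switch at the end of run-in (Protocol 5.1.4.1). If they keep the same reference week throughout, D loosely tracks further change since Visit 3, and a zero means no further change. This stands in part. The documents do not say whether the start of treatment means run-in or double-blind treatment, so D is hard to interpret but not meaningless.

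A reader might also infer that the subtraction adds noise and hides differences between arms. The documents do not support that. With equal variances and correlation r between the two ratings, Var(D)/Var(Y) = 2(1 − r). This is 1.4 at r = 0.3, 1.0 at r = 0.5 and 0.5 at r = 0.75. The plan gives no r, so even the direction is unknown. SAP 6.3 plans no model, confidence interval or test for PGI-C, and the unsubtracted ratings appear in the same summary.

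**Conclusion.** The point holds as a definitional fault. For both PGI-C items, the endpoint named in Protocol 6.4 and SAP 6.3 is a difference of two change ratings, and it matches the patient's own rating of change only when the Visit 3 rating is no change. This follows from the item descriptions in the protocol body and the rule in SAP 12.5. Only the numerical illustration rests on an assumed scale.

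The size is small. PGI-C lies outside the sixteen hypotheses under Type I error control (SAP 6.1.3), and no sample size, power or test decision depends on it. The practical consequence is that two PGI-C summaries will stand side by side, with the endpoint's name on the one that is harder to interpret.

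**What to change.** In SAP 6.3, for the daytime and night-time PGI-C:
- make the observed rating at Month 1 and Month 3, by arm and as category counts, the endpoint;
- drop the subtraction of the Visit 3 rating;
- show Visit 3 ratings only as a description of the run-in period.

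Record the departure from Protocol 6.4 in SAP 13.1, as was done for the PGA-S baseline.

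The cost is a text edit and one fewer derivation for two variables, with no new data and no sample-size work. A derived summary named in the protocol is given up, but change in severity since Visit 3 remains available from the PGA-S and PGI-S.

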6.4 Estimating minimal clinically important differences

This analysis will be described in a separate document and reported separately.

6.5 Patient preferences exploratory endpoints

This analysis will be described in a separate document and reported separately.

